- I. Data and/or specimens will not be transported or transmitted outside of Durham VAMC environment.
- II. Data and/or specimens will be transported BETWEEN sites that are under the auspices of the Durham VA Medical Center.
- III. Data and/or specimens will be transmitted to other VA sites using the following method(s):
 - A. Data
 - Data are de-identified and thus will be sent via unencrypted e-mail or unencrypted disk (encryption is optional).
 - Data are coded or contain identifiers and thus will be sent
 - Other, describe: Limited amount of PHI (such as task lists with study IDs) will be transported outside of the Durham VAMC environment. Those staff who will transport any PHI will complete a VASI form. Staff work in office and remotely with VA laptops. Electronic study data and information are retained within the VA environment.

B. Specimens

- Specimens are de-identified and thus will be sent via standard carrier (tracking is optional).
- Specimens are coded or contain identifiers and thus will be sent via VA-authorized carrier with tracking.
- Other, describe:

IV. Data and/or specimens will be transported to non-VA/VHA sites (e.g., academic affiliates, laboratories, etc.) using the following method(s):

A. Data

- Data are de-identified and thus will be sent via unencrypted e-mail or unencrypted CD.
- Data are coded or contain identifiers and thus will be sent via <choose method of transfer such as FIPS 140-2 encrypted CD or FIPS 140-2 encrypted hard drive/flash drive> using VA—approved carrier with tracking.
- Data are coded or identified and will be uploaded to sponsor website using electronic case report form (eCRF) <insert information including sponsor name and URL and the encryption the site uses.>
- Other, describe:

B. Specimens

- Specimens are de-identified and thus will be sent via standard carrier (tracking is optional) or will be hand-delivered by research study personnel. Specify method of delivery:
 - Specimens are coded and thus will be sent via VA-approved carrier with tracking or will be hand-delivered by research study personnel. Specify method of delivery:

In accordance with the HIPAA and the Privacy Act, for any coded or identifiable data or specimens released from the Durham VAMC (with the exception of Limited Data Sets), an Accounting of Disclosure (AOD) will be maintained (e.g., in a database or spreadsheet) that includes the participant's name, date of the disclosure, description of the nature of the Individually Identifiable Information (III) disclosed, purpose of each disclosure, and the name and address of the person/agency to whom the disclosure was made.

C. Local DVAMC memorandum "Authorization to Use, Process, Store, or Transmit VA Sensitive Information Outside VA Owned or Managed Facilities" has

been pre-filled out for each study team member who may transport the data and/or specimens off-site. These forms are included with the IRB materials.

D.

Containers (e.g., briefcase, bin) are labeled with the following notice (label placed on the outside of container) in accordance with VHA Directive 6609:

NOTICE!!!

Access to these records is limited to: AUTHORIZED PERSONS ONLY.
Information may not be disclosed from this file unless permitted by all applicable
legal authorities, which may include the Privacy Act; 38 U.S.C. §§ 5701, 5705,
7332; the Health Insurance Portability and Accountability Act; and regulations
implementing those provisions, at 38 C.F.R. §§ 1.460 – 1.599 and 45 C.F.R.
Parts 160 and 164. Anyone who discloses information in violation of the above
provisions may subject to civil and criminal penalties.

7. Risk Mitigation Strategies:

- Data are fully de-identified (stripped of HIPAA 18 and study ID/code) before being shared outside of Durham VAMC.
- Specimens are fully de-identified (stripped of HIPAA 18 and study ID/code before being shared outside of Durham VAMC.
- Direct identifiers will be maintained separately from data and or specimens by using a code to “identify” subjects. In a separate database (i.e., a “linking” or “cross-walk” database) this code will be linked to identifying subject information.

To mitigate the risk of unauthorized access, data will be stored behind the VA firewall with password protected access. The PI, individuals study coordinators and statistician will bear responsibility for overseeing the privacy and security of the data.

- Other, specify:

8. Suspected Loss of VA Information:

Should any incident such as theft or loss of data, unauthorized access of sensitive data or non-compliance with security controls occur it will be immediately reported according to VA policy. All incidents regarding information security/privacy incidents will be reported to the ISO and PO within 1 hour of acknowledgement of issue and done so using the VHADUR Research Events Report e-mail group ([contact]).

9. Reporting of Results:

Reporting of results, such as in scientific papers and presentations, will never identify individual subjects. For the quantitative aspects of the trial, Data will be presented in aggregate and individual-level data will not be published

In order for this research to have an impact, stakeholders, and those in position to effect change based on study findings, will be informed of the study findings. We also anticipate presenting the findings of this study at professional conferences with a focus on Sleep. The annual meetings for the following professional organizations are likely venues for these presentations: the HSR&D Annual Meeting; and the annual meetings of the American Academy of Sleep Medicine. Further, we are likely to produce several manuscripts describing the outcomes of the study. We expect manuscript preparation to begin following completion of the study.

Other results reporting plan, describe:

10. Future Use of Data:

Data will be retained for future use. This is described elsewhere in the protocol and is noted in the HIPAA authorization.

- Future Use of data is optional (i.e., not required by the research subject).
- Future Use of data is required for participation in the study.

No future use of data is currently planned.

11. Use of Mail Merge Technology

Mail merge programs will be used to generate letters and/or address labels for mailings to potential or already enrolled research subjects. The study team is aware that to reduce risk of mail merge related privacy incidents, use of mail merge programs requires a 25% accuracy check to verify that (potential) research subject name and mailing address are properly “matched”. If discrepancies are found, a 100% accuracy check is required before letters may be mailed.

12. Use of Non-Standard Software

I do NOT intend to use any new specialized software (i.e., Software that's not already approved OR installed) in this study.

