The target population for this trial is treatment-seeking Veterans with Insomnia from the Durham Veteran's Affairs Healthcare System. Because few VA PCPs routinely document insomnia in the medical record⁷⁹, identifying patients with insomnia in the EHR is challenging. Prescribed sleep medications are the most common PCP response to an insomnia complaint, although some patients are referred for CBTI. Consistent with the larger literature, we found no difference between Veterans prescribed sleep medications and those who were not prescribed sleep medications in terms of improvements in insomnia severity ($f=.15$, $p=.70$) following participation in group based CBTI at the Durham VAMC⁸⁰. Thus, we have defined treatment-seeking Veterans with Insomnia as those who are: a) prescribed sleep medications; b) diagnosed with insomnia; or c) referred for clinic-based CBTI (but not yet treated).

Table 1. Eligibility Criteria Assessment: Methods and Measures

Eligibility Criteria	Assessment Method
Level 1 (L1)-Data Pull and Chart Review	
Inclusion	
≥ 18 years of age	EHR data pull
Insomnia Diagnosis OR prescribed sleep medications OR referred for CBTI	EHR data pull & record review
Exclusion	
Psychotic DO; Bipolar DO; Substance Use; Alcohol Abuse	EHR data pull
Dementia; Cognitive Impairment; Epilepsy; Seizure DO	EHR data pull
Severe OSA with treatment non-adherence	EHR record review
Unstable housing and/or no/unreliable telephone	EHR record review
Unstable Co-morbid Sleep DO; and current or prior participation in CBTI	EHR record review
No current/prior CBTI participation	EHR record review
Nursing Home Residence	EHR record review
Level 2 (L2)-Phone Screening, Consent & Enrollment	
Inclusion	
Insomnia Disorder diagnostic criteria are met per ICSD-3	DSISD Insomnia DO Module ⁶
Insomnia Severity Index score of ≥ 10	ISI ⁷
Exclusion	
Severe OSA with treatment non-adherence (when unclear from EHR review)	Phone Screening
Unstable housing and/or no/unreliable telephone (when unclear from EHR review)	Phone Screening
Excessive daytime sleepiness	Epworth Sleepiness >15
Nighttime or Rotating Shift Work w/in the last year	Phone Screening
Confirm no current/prior CBTI participation	Phone Screening
Severe Depression and Suicidality	PHQ-8 >19 and/or SI
Current Recreational Drug Use	Drug Use Screener endorsed
Nursing Home Residence (to complement information from EHR chart review)	Phone Screening

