EHR=electronic health record; DO=Disorder; ICSD-3= International Classification of Sleep Disorders;
ISI=Insomnia Severity Index; OSA=Obstructive Sleep Apnea; PHQ=Patient Health Questionnaire; SI=Suicidal

Ideation.

C.3 Participant Selection and Recruitment

We plan to recruit Veterans using both CPRS record review and recruitment from the following clinics: Sleep Medicine Clinic; Behavioral Sleep Medicine Clinic; OEF/OIF/OND Clinic; Mental Health Clinics and Primary Care. We may utilize 1 or more of the following approaches to screen and recruit Veterans into the study:

Approach 1-EHR Recruitment

We will recruit treatment-seeking Veterans with Insomnia from the Durham VA Healthcare System using the criteria in Table 1. In Step 1, we will extract data from the EHR. Potentially eligible Veterans will be randomly selected from the data pull for chart review to identify those meeting Level 1 (L1) inclusion/exclusion criteria.

Veterans identified as eligible at Level 1 (L1 in Table 1) will receive a letter and Study Information sheet describing the study and offering the option to opt out of future study contacts. Those not opting out will receive a phone call to assess interest in the study. Interested Veterans will be screened for Level 2 (L2) criteria by phone (Veterans meeting these criteria and providing verbal informed consent will be invited to participate in the study. Veterans who are excluded from the study will be offered tailored interventions for insomnia through our Behavioral Sleep Medicine clinic and/or referred to our medical sleep clinic for additional assessment or treatment, as needed.

Approach 2-Provider-Assisted Recruitment

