her clinical work in the Behavioral Sleep Medicine (BSM) clinic; specifically, those who have been referred to the BSM Clinic and/or patients awaiting the availability of a provider to begin treatment. This will be accomplished by reviewing the chart of patients who have been referred to the BSM clinic with an insomnia complaint, and reviewing the BSM Clinic electronic waiting list/s. [name] will record in an excel file located here

(R:\Insomnia_Self_CBTI_Trial_IRB_2147\Data\Databases\Tracking Database\Physician Referrals) the name of patients meeting initial eligibility criteria (i.e., diagnosed with insomnia, prescribed sleep medications, and/or referred to the BSM clinic for insomnia treatment).

Research staff will then follow the recruitment procedures described in Approach 1 above, beginning with chart review.

Approach 3-Flyer Posting and Brochure Placement

Approach 3 involves placement of recruitment flyers in the VA approved research recruitment bulletin boards located throughout the hospital and CBOC clinics. We have also created a brochure about the study that may be distributed in clinics.

Exclusion criteria: 1) Severe Obstructive Sleep Apnea with treatment non-adherence; 2) unstable co-morbid sleep disorder determined via chart review (e.g., rule out for Narcolepsy, rule out for Shift Work Disorder); 3) current or prior participation in CBTI; 4) excessive daytime sleepiness; 5) nighttime or rotating shift work within the last year; 6) psychotic disorder diagnosis; 7) bipolar disorder diagnosis; 8) recreational substance use/abuse; 9) current alcohol abuse; 10) severe depression or suicidality; 11) dementia diagnosis; 12) cognitive impairment; 13) epilepsy or seizure disorder 14) lack of proficiency in the English language; 15) hearing impairment that impedes telehealth intervention; or lack of stable housing and/or no access to a telephone.

Rationale for Inclusion/Exclusion Criteria:

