Insomnia Disorder: To be eligible for this study, patients must meet diagnostic criteria for Insomnia Disorder (in accordance with the International Classification of Sleep Disorders-3 (ICSD-3) diagnostic criteria-e.g., at least 3 months of insomnia symptoms; daytime consequences of insomnia symptoms; and is not better explained by another condition). Since patients are often reticent to discuss insomnia with their providers until they have struggled with insomnia for some time, most treatment-seeking patients are likely to meet Insomnia Disorder diagnostic criteria. Still, by ensuring that diagnostic criteria are met we will exclude individuals: 1) with acute sleep difficulties that may resolve without intervention; 2) whose sleep complaints are the result of self-imposed sleep restriction (inadequate opportunity for sleep); and those whose symptoms are not at a frequency/severity which adversely impacts daytime functioning.

Excessive Daytime Sleepiness and Severe Untreated Sleep Apnea: Sleep restriction, an essential element of CBTI, is contraindicated in those with extreme daytime sleepiness. Since extreme sleepiness is common among those with severe untreated sleep apnea, they are not appropriate candidates for CBTI because they are unlikely to benefit from CBTI and need sleep apnea intervention (i.e., Positive Airway Pressure or other).

Rotating or Night Shift Work: Promoting a consistent sleep-wake schedule is a central treatment target of CBTI. As such, there is no empirical base supporting the use of CBTI among those engaged in Shift Work. Similarly, those engaged in night shift work are typically unable to entrain a consistent sleep schedule due to shifting back to a more typical sleep schedule, on weekends or when not working, to facilitate social interactions. As such, they are unlikely to benefit from standard CBTI without adjunctive circadian interventions. Thus, they will be excluded from participation.

Unstable Co-Morbid Sleep Disorders and Psychiatric Conditions: We are excluding those who are engaged in a process of being worked up for identification/diagnosis of sleep disorders and/or psychiatric disorders because our ability to determine eligibility criteria is hindered by the uncertainty of their condition, and the possibility that we might enroll someone who is later determined to be ineligible for the study.

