Psychotic Disorder and Cognitive Impairment: Individuals with these conditions will be excluded due to concerns regarding their ability to complete sleep diaries and to fully engage with treatment.

Bipolar Disorder: Sleep restriction can promote manic episodes in those with Bipolar Disorder. Thus, an essential element of CBTI (sleep restriction therapy) is contraindicated for this population.

Current Abuse of Alcohol and Recreational Drugs: Individuals engaged in substance abuse are excluded because they are unlikely to benefit from CBTI while using/abusing substances known to interfere with sleep.

Nursing Home Residence: Veterans living in nursing homes have little control of their sleep environment, which is an essential element of treatment. CBTI in these settings must be modified considerably.

Outside of Catchment area: Veterans living outside of the Durham VAMC catchment will be excluded because information in CPRS will not be adequate to screen for inclusion/exclusion criteria.

PCP Assignment: Patients without a Primary Care Physician assignment will be excluded because information in CPRS will not be adequate to screen for inclusion/exclusion criteria.

Unstable Housing: Veterans who do not have access to stable housing and/or a reliable telephone will be excluded because they may have an irregular sleep schedule or environment that would make controlling their sleep environment difficult in order to be adherent in treatment. A reliable phone is needed to complete this telephone-based study.

Veterans identified as eligible at Level 1 (L1 in Table 1) will receive a letter and Information Sheet describing the study and offering the option to opt out of future study contacts. Those not opting out will receive a phone call to assess interest in the study. Interested Veterans will be screened for Level 2 (L2) criteria by phone (See Appendix 2a-2f). Veterans meeting these criteria and providing verbal informed consent will be invited to participate in the study. For veterans who are excluded from the study but interested in further treatment for their sleep, the PI will place a clinic note to their PCP or MH provider and/or refer them to the Behavioral Sleep Medicine clinic for additional assessment or treatment, as needed.

C.4 Consent Process

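### The listed screening steps check bipolar disorder, for which the protocol calls sleep restriction contraindicated, only in the VA record; one phone question could identify some diagnoses the record does not hold.

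*Combined protocol and SAP*

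**What the plan says.** The exclusion list in C.3 includes "7) bipolar disorder diagnosis" and sets no limit on where the information comes from. The rationale in C.3 gives the reason: "Sleep restriction can promote manic episodes in those with Bipolar Disorder", and then "Thus, an essential element of CBTI (sleep restriction therapy) is contraindicated for this population". Table 5 delivers sleep restriction as the second of six Tele-Self CBTI modules.

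Table 1 sets out how each criterion is assessed. Bipolar disorder stands in the Level 1 row "Psychotic DO; Bipolar DO; Substance Use; Alcohol Abuse", and the method given is the EHR data pull. C.3 Approach 1 adds a chart review: "Potentially eligible Veterans will be randomly selected from the data pull for chart review to identify those meeting Level 1 (L1) inclusion/exclusion criteria". For Veterans referred by a clinician or found through the Behavioral Sleep Medicine clinic, C.3 says: "Research staff will then follow the recruitment procedures described in Approach 1 above, beginning with chart review".

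Two passages of the C.3 rationale restrict who can reach this point. One concerns diagnoses not yet settled: "We are excluding those who are engaged in a process of being worked up for identification/diagnosis of sleep disorders and/or psychiatric disorders". The other concerns how complete the record is: "Veterans living outside of the Durham VAMC catchment will be excluded because information in CPRS will not be adequate to screen". Veterans without an assigned primary care physician are excluded for the same reason.

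Section C.8 has current mental health conditions self-reported at baseline, in the paragraph on covariates. C.5 and Table 4 place randomisation after the baseline questionnaires.

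**The concern.** The protocol names a specific harm from one component of its own treatment and excludes the Veterans at risk of it. The listed check for that exclusion uses one source, the VA record. A diagnosis made outside the VA, or never charted, has no listed check. A Veteran with such a diagnosis who is assigned to Tele-Self CBTI would start sleep restriction in module 2. The safeguard described for the treatment period, nurses watching for serious adverse events (F.5), acts only once treatment has begun. The withdrawal rule in F.4 concerns suicidal ideation. What is at stake is the safety of a few participants; the estimate and the test are not affected.

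**Working it through.** The plan gives no figure on this point, so there is none to reproduce. The check is a comparison of the listed methods, followed by simple arithmetic on scale.

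**1. How comparable exclusions are checked (Table 1).**

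| Exclusion | VA record (Level 1) | Phone (Level 2) |
|---|---|---|
| Severe sleep apnea, treatment not followed | yes | yes, if the record is unclear |
| Unstable housing or unreliable telephone | yes | yes, if the record is unclear |
| Current or prior CBTI | yes | yes |
| Nursing home residence | yes | yes, to supplement the record |
| Recreational drug use | yes, as substance use | yes, screening item |
| Excessive daytime sleepiness | no | yes, Epworth above 15 |
| Bipolar disorder | yes | none listed |

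The first four rows are the record-based exclusions that are asked about again. The rationale ties one other condition to a contraindication for sleep restriction, extreme daytime sleepiness, and that one gets a direct phone instrument.

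**2. Content of the phone screen.** Table 1 has eight Level 2 exclusion rows, none on bipolar disorder or mania. The Table 4 screening row lists seven items: shift work, drug use, prior CBTI, DSISD, Epworth, ISI and PHQ-8. None of the seven asks about bipolar disorder. C.8 limits the DSISD to its insomnia module and uses the PHQ-8 for depression.

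**3. Who is left.** A charted diagnosis should be found, because chart review covers the Level 1 criteria. Veterans outside the catchment, without a primary care physician or in psychiatric work-up are excluded, though Table 1 lists no phone step for these either. The remaining group is in-catchment Veterans with a primary care physician whose diagnosis is settled and known to them but absent from the VA record.

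**4. Scale, on assumption only.** The Tele-Self CBTI arm has 200 × 1/2 = 100 Veterans. Let r be the share of those randomised who have an unrecorded diagnosis; the documents give no value. Expected number in the arm = 100r. Chance of at least one = 1 − (1 − r)^100.

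- r = 0.1%: 0.1 expected; chance 9.5%
- r = 0.5%: 0.5 expected; chance 39%
- r = 1%: 1 expected; chance 63%
- r = 2%: 2 expected; chance 87%

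If a phone question found a share s of them, the expected number would become 100r(1 − s)/(1 − rs). With r = 1%, that is 0.50 at s = 50% and 0.10 at s = 90% (both values of s assumed). The question reduces the number but does not bring it to zero.

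**5. Effect on the planned size.** The question comes before randomisation, so 200 are still randomised and the planned power is unchanged. If every unrecorded case were found, the extra Veterans needed to pass the other screens would be 200/(1 − r) − 200, which is 0.2 at r = 0.1% and 4.1 at r = 2%.

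**The case against.** The strongest reply is that the tables are not complete. Table 1 assigns sleep apnea adherence, housing and nursing home residence to the phone screen, yet Table 4 lists none of them. English proficiency and hearing impairment are exclusions with no listed method at all. The call therefore covers more than the tables show, and its scripts are in Appendix 2a-2f, which was not available. This stands: the point is limited to the listed procedures, and the fix is conditional.

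Other information also arrives before randomisation. C.5 stratifies on whether a mental health disorder is present, the DSISD considers whether another condition explains the insomnia better, and mental health conditions are self-reported at baseline. None of these is specific to bipolar disorder. Table 3 places mental health conditions under record data, so it is unclear whether the Comorbidity Questionnaire names bipolar disorder.

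The VA record is also broad: progress notes, mental health notes and psychotropic medication could reveal an outside diagnosis. That makes the group smaller, but it is still the same record. Other psychiatric and neurological diagnoses are checked from the record too, so the method is consistent. For psychotic disorder and cognitive impairment, however, the stated reason is ability to keep diaries and take part, whereas for bipolar disorder it is harm from the treatment.

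Four stronger readings are tempting, and the documents do not support them:

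- Referred Veterans, or those answering a flyer, might seem to bypass the bipolar check because Table 1 names only the data pull. Chart review covers the Level 1 criteria, the referral and clinic routes start there, and the data acquisition item of the privacy section describes chart review plus phone screening without limiting it by route.
- A Veteran who disclosed the diagnosis at baseline might seem bound to be randomised. Exclusion 7 has no source limit and would apply; all that is missing is an explicit step to check the answers.
- One question might seem to close the gap. It reaches only diagnoses the Veteran knows of and reports.
- The 9.5% to 87% range might be read as an estimate of risk. It reflects only the assumed r, and the documents give no rate of mania under sleep restriction.

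**Conclusion.** The point holds for the listed methods. Bipolar disorder is assessed only from the VA record, while the protocol itself calls a module of the treatment contraindicated there and uses the telephone to back up or screen other exclusions. A Veteran with a known but unrecorded diagnosis could pass every listed step. The number is probably small and cannot be estimated from the documents. The conclusion rests on Tables 1 and 4 as published and would fall away if the phone script already asks the question. This is a cheap safety improvement. It is not an error in the analysis, and it does not show that any participant has been harmed.

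**What to change.** First check whether Appendix 2a-2f already contains the question. If it does, list it in Tables 1 and 4. If not, add one Level 2 item to both: whether a health professional has ever told the Veteran that they have bipolar disorder or manic-depressive illness. State in C.5 that a positive answer, or a bipolar disclosure in the baseline data, is reviewed against exclusion 7 by one of the existing study clinicians before randomisation. The baseline part mostly makes explicit what exclusion 7 already implies; the phone question is the substantive change. A positive answer leads to review and does not exclude by itself, so the eligibility criteria stay as they are.

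The cost is an amendment and, if the question takes under a minute (assumption), at most 1/30 = 3.3% of the 30-minute screening call in Table 4. There would be a few clinician reviews, some prompted by mistaken self-report, and a few more screen failures.
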